This material is the property of Ochsner Clinic Foundation. Do not disclose or use except as authorized in writing by the study sponsor

9.1	CONFIDENTIALITY.....	12
9.2	SOURCE DOCUMENTS.....	12
9.3	RECORDS RETENTION	13
10	STUDY MONITORING, AUDITING, AND INSPECTING	13
10.1	STUDY MONITORING PLAN	13
10.2	AUDITING AND INSPECTING.....	13
11	ETHICAL CONSIDERATIONS.....	13
12	STUDY FINANCES.....	14
12.1	FUNDING SOURCE	14
12.2	CONFLICT OF INTEREST	14
12.3	SUBJECT STIPENDS OR PAYMENTS	14
13	PUBLICATION PLAN.....	14
14	REFERENCES.....	15
15	ATTACHMENTS	16

CONFIDENTIAL

This material is the property of Ochsner Clinic Foundation. Do not disclose or use except as authorized in writing by the study sponsor

List of Abbreviations

CRS- Chronic Rhinosinusitis

IA- Inhaled Anesthesia

PONV- Postoperative nausea and vomiting

TIVA- Total Intravenous Anesthesia

CONFIDENTIAL

This material is the property of Ochsner Clinic Foundation. Do not disclose or use except as authorized in writing by the study sponsor

Study Summary

Title	Total Intravenous versus Inhaled Anesthesia in Endoscopic Sinus Surgery for Advanced Paranasal Disease
Short Title	TIVA in high-risk endoscopic sinus surgery
Protocol Number	Pro00011453
Phase	
Methodology	Randomized controlled trial
Study Duration	18 months
Study Center(s)	Ochsner Clinic Foundation
Objectives	Evaluate the role of TIVA for maintenance of anesthesia during endoscopic sinus surgery. Outcome measures of operative visual field, change in sinus related quality-of-life, surgical time, complications and postoperative nausea and vomiting will be collected with subgroup analysis of patients with advanced paranasal sinus disease.
Number of Subjects	110
Diagnosis and Main Inclusion Criteria	Chronic rhinosinusitis. English speaking patients undergoing endoscopic sinus surgery for treatment of inflammatory paranasal sinus disease.
Study Product, Dose, Route, Regimen	Propofol, 100-200 mcg/kg/min IV for maintenance of anesthesia with goal mean arterial pressure of 70-80 mmHg
Duration of administration	Limited to maintenance of anesthesia during endoscopic sinus surgery
Reference therapy	Inhaled anesthesia

Statistical Methodology	All parametric data is tested for normal distribution and characterized by mean +/- standard deviation. Differences between the visual field and change in quality-of-life measure for the two treatment groups are evaluated using a t -test. The association between the treatment groups and surgical procedure is tested using the chi-square test. The association between the treatment groups and pathological groups is tested using Fisher's exact test.
-------------------------	--

CONFIDENTIAL

This material is the property of Ochsner Clinic Foundation. Do not disclose or use except as authorized in writing by the study sponsor

1 Introduction

This document is a protocol for a human research study. This study is to be conducted according to US and international standards of Good Clinical Practice (FDA Title 21 part 312 and International Conference on Harmonization guidelines), applicable government regulations and Institutional research policies and procedures.

1.1 *Background*

Successful endoscopic sinus surgery (ESS) is largely dependent on identification of anatomic landmarks within a visually limited surgical field. Tight structural spaces, inflammatory tissues and intraoperative bleeding combine to decrease surgical exposure, with resultant increases in operative time, total blood loss and intraoperative complications. Maneuvers to improve the endoscopic visual field include reverse Trendelenburg positioning, nasal decongestion and infiltration of the lateral nasal wall with vasoactive epinephrine, and are currently accepted as standard of care¹. Utilization of total intravenous anesthesia (TIVA) has been proposed as an additional method to improve visualization during ESS, largely due to its physiologic decrease in cardiac output without the peripheral smooth muscle relaxation and resultant vasodilation associated with inhaled anesthetics (IA)². Propofol, when utilized for maintenance of anesthesia, is associated with decreased blood loss in several orthopedic and obstetric procedures³⁻⁵. However, despite this physiologic basis for improved intraoperative visualization with TIVA, conclusive evidence remains elusive⁶⁻¹⁰. While two recently published meta-analyses cite suggestive evidence for improved visual fields in ESS with TIVA, definitive recommendations could not be made due to limitations in the constituent studies^{11, 12}. The objective of this study is therefore to evaluate the effects of TIVA versus IA on intraoperative visual field in ESS.

This application seeks to improve clinical practice paradigms by evaluating the use of TIVA for maintenance of anesthesia in ESS for advanced paranasal sinus disease. Despite several previous studies evaluating the effect of TIVA on endoscopic visual field in ESS, limited study sizes and heterogeneous outcome measures prevent definitive recommendations. Additionally, the role of TIVA has not been reported among a subset of patients with advanced paranasal sinus disease. This study seeks to address these concerns, and will utilize the validated Wormald Visual Scale¹³ as a standardized outcome measure with the sensitivity to detect changes in visual field not recognized by other means (Boezaart Grading Scale, total blood loss).

CONFIDENTIAL

This material is the property of Ochsner Clinic Foundation. Do not disclose or use except as authorized in writing by the study sponsor

Investigational Agent
Propofol (Diprivan)

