3.3 Secondary Study Endpoints

Secondary outcome measures include change in sinus-related quality-of-life, intraoperative bleeding, surgical time, post anesthesia care unit recovery time, postoperative nausea and vomiting (PONV), complications and response duration.

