All patients are placed in 30 degree Reverse Trendelenberg positioning. 10 minutes prior to start of surgery, patients are pretreated with 4% cocaine-soaked nasal pledgets and local injection of 1% xylocaine with 1:100,000 epinephrine into the submucosa at the anterior attachment of the middle turbinate and crista ethmoidalis. Topical thrombin and epinephrine soaked pledgets will be available for intraoperative maintenance of hemostasis. Endoscopic sinus surgery will be completed following the modified Messerklinger technique, with utilization of endoscopic surgical equipment for video documentation of the surgical field. Recording equipment includes the Storz 4mm 0° rigid endoscope (Karl Storz, Tuttlingen, Germany) connected to a high definition camera and Olympus Evis Extra II light source. The video is recorded in MPEG2 digital format and transferred to the password protected study database. Visual field is recorded following the standardized method reported by Wormald et al., with the protocol as follows:

Prior to completion of surgery, old blood is suctioned from the nasal cavity with care not to traumatize mucosal surfaces and reinitiate bleeding. The surgical field is then recorded in a systematic fashion, with observation of four intranasal structures. Moving from anterior/superior to posterior/inferior, the frontal recess, ethmoidal cavity (endoscope positioned just anterior to the middle meatus), sphenoidal recess, and postnasal space are serially recorded for ten seconds each.

Following completion of surgery total blood loss will be calculated by the nursing circulator, with subtraction of the volume of intraoperative irrigation from the total volume contained in all suction canisters and saturated towels. The patient will be transferred to post-operative recovery and released home upon meeting established criteria. Patients will undergo routine postoperative follow-up, with evaluation at 1, 2, 4 weeks and as needed. A new SNOT-22 questionnaire will be completed as part of the postoperative week 2 and 4 visit.

CONFIDENTIAL

This material is the property of Ochsner Clinic Foundation. Do not disclose or use except as authorized in writing by the study sponsor

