5.9.3 Dispensing of Study Drug

Staff anesthesiologists will dispense study drug in the perioperative setting. Drug administration will be recorded and maintained in the surgical record.

6 Study Procedures

Participants make no clinic/hospital visits for purposes of study completion as all patient interaction limited to visits and surveys completed as part of routine clinical care.

6.1 Visit 1

Clinic presentation: A 22-item Sinonasal Outcome Test (SNOT-22) survey is completed per routine clinical care. Patients considering endoscopic sinus surgery for treatment of inflammatory paranasal sinus disease are initially screened for study participation. The principal investigator ([name]) presents the research purpose, personnel, procedures, risks and benefits of the study, and provides a written copy of the study consent for home review.

6.2 Visit 2

Preoperative visit: Study consent reviewed with an investigator and signed at this time. Enrolled patients will be assigned a randomly generated unique study identification number. The patient's demographic information will then be entered into the password-protected study database (Excel, Microsoft, Redwood, WA), which will be maintained on a HIPAA compliant server with access restricted to identified study computer maintained in the department of Otolaryngology.

6.3 Visit 3

Day of Surgery: Study consent reviewed and treatment group assigned. Intervention limited to perioperative maintenance of anesthesia with recording of deidentified endonasal endoscopic video for independent analysis of surgical visual field.

6.4 Visit 4

Routine 1-week postoperative follow-up.

6.5 Visit 5

Routine follow-up 4 weeks after date of surgery with completion of SNOT-22 survey.

6.6 Visit 5

Routine follow-up 12 weeks after date of surgery with completion of SNOT-22 survey.

CONFIDENTIAL

This material is the property of Ochsner Clinic Foundation. Do not disclose or use except as authorized in writing by the study sponsor

7 Statistical Plan

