7.2 Subject Population(s) for Analysis

Subgroup analysis will be completed of patients deemed “high risk” for endoscopic sinus surgery. This includes patients with diagnoses of allergic fungal sinusitis, CRS with nasal polyposis, CRS with eosinophilia and advanced paranasal sinus disease (LM>12). The analysis plan has been reviewed by an in-house statistician.

8 Safety and Adverse Events

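### Change in SNOT-22, a secondary endpoint, is compared by an unadjusted t-test although baseline SNOT-22 is collected; ANCOVA on baseline would usually be more precise and at worst about 1% less so

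*Combined protocol and SAP*

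**What the plan says.** Section 3.3 sets the endpoint: "Secondary outcome measures include change in sinus-related quality-of-life". SNOT-22 is the only quality-of-life instrument the protocol names.

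The analysis is given once, under Statistical Methodology in the Study Summary: "Differences between the visual field and change in quality-of-life measure for the two treatment groups are evaluated using a" t-test. Section 7 covers only the sample size and the subgroups. Neither place names a covariate or an adjusted model.

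The baseline score is available. Section 6.1 (Visit 1) states: "A 22-item Sinonasal Outcome Test (SNOT-22) survey is completed per routine clinical care". Treatment is assigned later, on the day of surgery (sections 5.3 and 6.3), so the Visit 1 score is a genuine pre-randomisation covariate.

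The follow-up scores are scheduled in two ways:
- Section 5.2, Surgical Protocol: "A new SNOT-22 questionnaire will be completed as part of the postoperative week 2 and 4 visit".
- Section 6.5: "Routine follow-up 4 weeks after date of surgery with completion of SNOT-22 survey"; section 6.6: "Routine follow-up 12 weeks after date of surgery with completion of SNOT-22 survey".

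**The concern.** A change score uses the baseline, but with a fixed weight of 1. The weight that minimises the variance is the regression slope of follow-up on baseline, which equals k times r, where k is the follow-up SD divided by the baseline SD and r is their correlation. Unless that product happens to be close to 1, subtracting the whole baseline leaves avoidable noise in the comparison.

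The trial was sized on visual field, so the number of patients available for SNOT-22 is fixed by another endpoint. How the baseline enters the analysis is one of the few ways left to sharpen that comparison. What is at stake is the width of one secondary confidence interval. Leaving adjustment unspecified also means that it could be chosen after the results are known.

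**Working it through.** **Inputs.** Section 7.1 gives 52 per arm, 104 in total, raised to 110 for dropout. That calculation concerns visual field. The plan gives no power, SD or effect size for SNOT-22, so there is no figure of its own to reproduce here. The values of r and k are not in the documents; r of 0.3 to 0.7 and k of 0.8 to 1.4 are assumptions.

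**Formulas.** Set the baseline SD to 1, so that the follow-up SD is k.
- Variance of the change: 1 + k² − 2kr.
- Residual variance after regression on baseline: k²(1 − r²).
- The first minus the second is (1 − kr)². It is never negative, and it is zero only when kr = 1.
- Variance ratio, ANCOVA to change: k²(1 − r²) / (1 + k² − 2kr). At k = 1 this is (1 + r)/2.
- Cost of estimating one slope: multiply by 1 + 1/(N − 4). At N = 104 this is 1 + 1/100 = 1.01.

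**Worked examples.**
- k = 1, r = 0.3: 1.3/2 × 1.01 = 0.657, a reduction of about 34%.
- k = 1, r = 0.7: 1.7/2 × 1.01 = 0.859, a reduction of about 14%.
- k = 1.4, r = 0.7: (1.96 × 0.51)/(1 + 1.96 − 1.96) × 1.01 = 0.9996 × 1.01 = 1.010, a loss of about 1%.

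**Variance ratios, including the factor 1.01:**

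| k | r = 0.3 | r = 0.5 | r = 0.7 |
|---|---|---|---|
| 0.8 | 0.507 | 0.577 | 0.634 |
| 1.0 | 0.657 | 0.758 | 0.859 |
| 1.2 | 0.770 | 0.880 | 0.976 |

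The extremes over this range lie at the corners: reductions of 49.3% (k = 0.8, r = 0.3) and 2.4% (k = 1.2, r = 0.7).

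**In terms of the 95% CI.** Its width scales with the square root of the ratio. At k = 1 it narrows by 1 − √0.657 = 19% down to 1 − √0.859 = 7%. At the two extremes it narrows by 1 − √0.507 = 29% and 1 − √0.976 = 1%.

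**Where nothing is gained.** With r = 0.7 the ratio is 1.001 at k = 1.3 and 1.010 at k = 1.4. At k = 1.2 ANCOVA is slightly worse for r of about 0.77 to 0.88. Because the ratio before the slope factor cannot exceed 1, the loss cannot exceed about 1% at N = 104.

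**Simulation check.** With 52 per arm and 40,000 trials per case, the reductions were 34.2% and 14.1% at k = 1 (r = 0.3 and 0.7), 49.0% at k = 0.8 with r = 0.3, and 2.5% at k = 1.2 with r = 0.7. These agree with the formula.

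**Missing follow-up.** With 45 complete pairs per arm the factor is 1 + 1/86 = 1.012. The reductions become 34.2% to 14.0% at k = 1, and 2.2% to 49.2% over k of 0.8 to 1.2. Attrition hardly changes the comparison of the two methods.

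**The case against.** The plan contains no error on this point. A t-test on change answers the endpoint as section 3.3 words it, and it is valid under randomisation. Only one of several secondary endpoints is affected. All of that stands, and it limits the point to an efficiency gain.

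The size of the gain rests on assumed values. The documents do not show which r and k are plausible, and the SD after surgery could move either way. A range of 2% to 49% runs from negligible to large, and a cut-off at k = 1.2 leaves out cases with no gain. This also stands: the percentages are illustrations, and a reader should not infer that the planned interval is materially too wide. The recommendation survives because it does not depend on knowing r and k, as the loss is bounded at about 1%.

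The unresolved follow-up visit is arguably the more serious defect, since r and k may differ by visit. That is a reason to settle the visit first, not to leave the baseline out of the model.

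A reader might also infer that the primary visual-field t-test should be adjusted for preoperative severity. The Background says "Tight structural spaces, inflammatory tissues and intraoperative bleeding combine to decrease surgical exposure", and section 7.2 defines a high-risk group: "This includes patients with diagnoses of allergic fungal sinusitis, CRS with nasal polyposis, CRS with eosinophilia and advanced paranasal sinus disease (LM>12"). The documents do not support that step. They give no correlation between preoperative severity and the visual field score. Section 7.2 lists several routes into one group, which does not establish that each characteristic is recorded before surgery for every patient. If severity explained nothing, adjusting for two covariates would lower an assumed power of 80% to 79.2%.

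**Conclusion.** The point holds as lost precision on a secondary endpoint. A baseline score already collected before randomisation is used only with a fixed weight of 1. It does not hold as a claim of bias, and it does not touch type I error, the primary analysis or the sample size of 104 (110 with dropout).

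The size is conditional on r and k, which the documents do not give. Within the assumed ranges the variance reduction runs from worthwhile to negligible, and it vanishes as kr approaches 1. What does not depend on those values is the asymmetry: a possible gain, sometimes large, against a loss of at most about 1%. That justifies a recommended change, not a mandatory one. Confidence is medium, because the actual gain in this trial cannot be determined from the documents.

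**What to change.** 1. Reconcile the SNOT-22 schedule. Section 5.2 has weeks 2 and 4; sections 6.5 and 6.6 have weeks 4 and 12. Week 4 is the only visit common to both. Then name one analysis visit for the quality-of-life endpoint.
2. State that SNOT-22 at that visit is analysed by ANCOVA, with treatment and baseline SNOT-22 in the model, and report the adjusted difference with its 95% CI. With baseline as a covariate, modelling the follow-up score or the change gives the same treatment difference, so the endpoint of section 3.3 is kept.
3. Keep the t-test on change as a supportive analysis.
4. Make the change before unblinding. Leave the visual-field analysis as it is on this point.

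The cost is SAP wording. The baseline and follow-up scores are already planned, and no extra patients are needed. The worst statistical outcome is about 1% more variance at N = 104.

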3.4 Primary Safety Endpoints

Safety endpoints include adverse surgical (intraoperative orbital/dural injury and postoperative hemorrhage/cerebrospinal fluid leak) and pharmacologic (severe PONV) events.

4 Subject Selection and Withdrawal

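### Procedure and pathology are tested against treatment arm but left out of the outcome comparison, where adjusting for them at baseline would add precision cheaply

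*Combined protocol and SAP*

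**What the plan says.** The Statistical Methodology row of the Study Summary assigns three tests.

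- Outcomes: "Differences between the visual field and change in quality-of-life measure for the two treatment groups are evaluated using a" t-test. No covariate or stratification factor is named.
- Procedure: "The association between the treatment groups and surgical procedure is tested using the chi-square test".
- Pathology: "The association between the treatment groups and pathological groups is tested using Fisher's exact test".

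Section 7 adds a sample size (7.1) and a high-risk subgroup analysis (7.2). On the subgroup, 7.2 says: "This includes patients with diagnoses of allergic fungal sinusitis, CRS with nasal polyposis, CRS with eosinophilia and advanced paranasal sinus disease (LM>12"). Disease status therefore enters the analysis only through that subgroup.

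Section 5.3 allocates by sealed envelope opened on the day of surgery. Sections 5.3 and 5.8 keep the surgeon unaware of the arm.

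Section 3.3 lists as secondary outcomes "change in sinus-related quality-of-life, intraoperative bleeding, surgical time, post anesthesia care unit recovery time", followed by PONV, complications and response duration. Section 3.4 makes severe PONV and surgical injuries the safety endpoints. Of all these, only change in quality of life has a named test.

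**The concern.** Extent of disease and extent of surgery are plausible predictors of the visual field. Section 1.1 itself says that confined anatomy, inflamed tissue and bleeding reduce exposure and lengthen the operation. The plan collects these variables but uses them only to ask whether the arms differ on them.

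For a characteristic fixed before the envelope is opened, that question has a known answer under random allocation: any difference is chance. A significant p-value would not show that the treatment comparison is distorted. A non-significant one would not show that an imbalance in a strongly prognostic factor is negligible. The plan attaches no action to either result.

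At stake is precision in the primary comparison, and in surgical time and blood loss, in a trial of about 52 patients per arm.

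**Working it through.** **1. Which variables precede allocation?** The patient's disease precedes it. Surgical procedure is not defined. If it means the planned operation, it precedes allocation and can be a covariate. If it means the operation performed, it follows allocation and the visual field could influence it. It is then neither a balance check nor a suitable covariate. Surgeon blinding limits that influence but does not exclude it.

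**2. How often would the two tests raise a false alarm?** If both nulls are true and the tests are independent at exactly 5%, the chance of at least one significant result is 1 − 0.95² = 0.0975. This is an upper figure, because Fisher's test is conservative. A simulation of 4,000 randomisations at 52 per arm, with assumed category mixes, gave 5.0% for chi-square, 2.9% for Fisher and 7.8% for either.

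**3. The plan's own sample size.** Section 7.1 states 52 per cohort, 104 in total, raised to 110 for dropout. The 52 cannot be reproduced, because no difference, SD, alpha, sidedness or power is given. Assuming two-sided 5% and 80% power, 52 per arm corresponds to a standardised difference of (1.960 + 0.842) × √(2/52) = 0.549 by the normal approximation, or 0.555 by the t distribution. I use 0.555 as the assumed starting point.

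**4. Effect of adjustment.** Baseline covariates that explain a share R² of the outcome variance shrink the residual SD by √(1 − R²). The standardised difference becomes d' = 0.555/√(1 − R²), with noncentrality d' × √(52/2). The equivalent gain in patients is 1/(1 − R²) − 1. The R² values are assumptions; the documents give none.

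| R² (assumed) | d' | Noncentrality | Power | Equivalent gain in patients |
|---|---|---|---|---|
| 0 | 0.555 | 2.83 | 80% | 0% |
| 0.1 | 0.585 | 2.98 | 84% | 11% |
| 0.2 | 0.621 | 3.16 | 88% | 25% |
| 0.3 | 0.663 | 3.38 | 92% | 43% |

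The normal approximation from 0.549 gives the same rounded powers. Spending up to six degrees of freedom on covariates lowers each power by less than 0.1 percentage point.

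**5. Binary outcomes.** At 52 per arm and two-sided 5%, with assumed rates, power is 45% for PONV of 30% against 15%, and 22% for complications of 5% against 1%. An estimate with an interval would tell the reader more here than a p-value.

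**The case against.** The strongest reply is that an unadjusted t-test in a randomised trial is valid and that baseline tests are customary, so nothing in the primary result is wrong. That stands: this is an efficiency point, and removing the two balance tests changes no result.

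Several stronger readings are tempting, but the documents do not support them.

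- A reader might infer that randomisation makes both nulls true. That follows for disease group, but for procedure only if the planned operation is meant.
- A reader might take 9.75% as the false-alarm rate. It needs two true nulls, exact 5% tests and independence. Fisher's test falls below 5%, and disease extent plausibly drives the choice of procedure.
- A reader might say the tests can serve no purpose. They could flag failed allocation, and the plan does not describe how the sequence is generated. Withdrawn subjects also give no further data (section 4.4.2), so the analysed groups may differ from those randomised. The plan, however, states no such purpose.
- A reader might conclude that patients would be counted more than once. Section 7.2 defines high risk, not the pathological groups of the Study Summary. Overlap is possible but not shown.
- A reader might see the absent tests for PONV and complications as the main fault. They are mainly missing detail, part of a wider gap that also covers surgical time, blood loss, recovery time and response duration.

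It is also fair to say that the power gain illustrates a general property of adjustment. It does not measure a loss in this trial.

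**Conclusion.** The point holds as one about precision. The plan tests prognostic variables against arm and leaves them out of the model in which they would help. The primary comparison is not biased as it stands.

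The gain is from an assumed 80% to about 84% to 92% power, for covariates explaining an assumed 10% to 30% of the variance. Apart from the 52 per arm, every input is an assumption: 0.555 SD, two-sided 5%, 80% and R². The documents support only the direction, through the account in section 1.1 of what limits exposure. If the covariates explain little, the gain is small, and so is the cost.

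**What to change.** 1. Replace the two association tests with a table of pathology and procedure by arm, without p-values. State whether procedure means planned or performed.
2. Estimate the arm difference in visual field, surgical time and blood loss from linear models with two baseline covariates, and report each difference with a confidence interval. The first covariate is high-risk status (a diagnosis listed in section 7.2, or LM>12), which the subgroup analysis needs anyway. The second is planned extent of surgery, recorded before the envelope is opened, for example at Visit 2. Classify both from information available before allocation, and fix their coding in advance. Do not adjust for the operation performed.
3. Keep the unadjusted t-test for visual field as a sensitivity analysis.
4. For PONV and complications, define the event, then report counts by arm with a risk difference and confidence interval.

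The cost is revised analysis wording, a few degrees of freedom depending on coding, and possibly one added baseline field. Attachment C, the table of collected data, is not in the text available, so planned procedure may already be recorded. No extra patients are needed.
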